2.2. Participants

Participants will include BC survivors who: experience symptoms of insomnia, self-report to be nonadherent to their ET medication, are fluent in English, and have access to videoconferencing software. Treatment nonadherence and insomnia symptoms will be established first during the screening interview, and at baseline, by responses to the Medication Adherence Report Scale (MARS-5) and Sleep Condition Indicator (SCI), respectively, using established cut-off scores.

Exclusion criteria include: individuals who are currently pregnant or breastfeeding, have received CBT-I within the past 12 months, have received chemotherapy or radiotherapy within the past 4 weeks or have plans for future treatment, struggle with substance misuse, or have an unstable physical or mental health condition (e.g. psychosis) which would be incompatible with CBT-I treatment.

Participants will not be excluded on the basis of other sleep disorders, if they report that these are stable and well-managed. Participants will not be excluded on the basis of a palliative BC treatment plan. However, during the screening interview the nature of CBT-I treatment will be explained to them, as this treatment can be difficult to implement, and they will be asked if they feel well enough to participate.

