2.2.1. Recruitment

We will aim to recruit a sample of 40 participants. A-priori power analysis was conducted using G*Power version 3.1.9.7 (Faul et al., 2007) to determine the minimum sample size required to test the study hypothesis using a repeated measures ANOVA (within-between interaction). Results indicated the required sample size to achieve 80% power for detecting a medium effect (significance criterion α =.05) was *N*=18. Therefore, the target sample size of *N*=40 is adequate to test the study hypothesis.

Recruitment will involve emailing participants of a previous study (UEC21/29) who indicated that they would be interested in participation in future research studies. We will contact individuals from this sample whose responses indicated they are nonadherent to their ET medication and experience significant sleep problems, informing them of the opportunity to take part in this study.

The initial email will briefly outline the nature of the study and include an information sheet with full study details. Those who are interested will be asked to respond to this initial email so that a screening interview can be scheduled.

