2.3. Procedure

Those who indicate interest in participation will be emailed a link to a virtual consent form via Qualtrics survey platform. Following informed consent, a screening interview will be scheduled. They will then be interviewed to ensure eligibility criteria are met. Screening interviews will be carried out by the PhD student: if there are any points of uncertainty, clarification will be sought through discussion with academic supervisors. Those who meet inclusion criteria following screening will be sent a link to the baseline assessment, then randomised to either the intervention or waitlist control group. All further assessments will be sent via email and carried out through Qualtrics survey platform.

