2.4. Randomisation

Participants will be allocated on a 2:1 basis to the waitlist or intervention group. The study team will have no influence over the randomisation process. Participants will be randomised using block randomisation in blocks of 10. The advantage of this method is that it maintains balance between intervention and control group, as significant imbalance would reduce the power of the study in a small sample (Lim & In, 2019; Pinto et al., 2022).

Upon providing informed consent, participants will be assigned a unique identifier (UID). A PhD student unrelated to the study will be given a list of these UIDs and use an online randomisation tool to generate an allocation sequence, which will be used to assign each group's participants. They will then pass the list of UIDs assigned to each group to the PhD student for the study, who will establish which participants are in each group. Following randomisation, the intervention group will be emailed a recurring link to access CBT-I sessions via videoconferencing.

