2.5. Intervention

CBT-I is a multi-component, evidence-based intervention which incorporates both cognitive and behavioural techniques to address symptoms of insomnia, aiming to improve satisfaction with the duration and quality of sleep by reducing trouble falling and/or staying asleep. Its main components include: sleep restriction, stimulus control, and cognitive restructuring. Sleep restriction aims to reduce discrepancy between time spent in bed and time actually sleeping by improving 'sleep efficiency' (SE), which is the time spent sleeping expressed as a percentage of time spent in bed. The individual is given a prescribed bedtime and waketime to match their time spent in bed with time sleeping, which is adjusted accordingly when their SE reaches 90%, or falls below 85%. Stimulus control involves strengthening the association between being in bed and being asleep, by minimising activity in the bed unrelated to sleep or intimacy, getting out of bed if unable to initiate sleep or get back to sleep after waking up, and only returning to bed when sleepy. Cognitive restructuring challenges maladaptive beliefs about sleep and concerns about the daytime consequences of poor sleep, to reduce arousal and anxiety associated with insomnia.

CBT-I will be delivered over 4 weekly 1-hour sessions, via videoconferencing. Session 1 will include psychoeducation about sleep (the relationship between sleep and mental health, the '3P' model of insomnia), and begin to explain components of CBT-I (sleep restriction and relaxation). Session 2 will reinforce previous learning about these components and introduce stimulus control. Session 3 will introduce sleep hygiene and its importance in preventing poor sleep. Session will 4 discuss cognitive therapy techniques and relapse prevention.

Participants in the waitlist condition will receive the CBT-I intervention after completing the 12-week follow-up assessment. This will then be used as a baseline measure for these participants to compare to their post-intervention and follow-up after receiving the treatment.

The intervention will be delivered by a PhD student, who will receive extensive CBT-I training from supervisors who have over 15 years' experience in delivering CBT-I. The student will receive continuous supervision throughout. Sessions will be recorded and 10% will be assessed by supervisors to monitor treatment fidelity.

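### With one fixed block size of 10 known to the study team, later allocations can be foreseen if lists are released before a block is complete; section 2.4 does not rule this out

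*Combined protocol and SAP*

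**What the plan says.** Protocol section 2.4 (Randomisation) sets the ratio, "Participants will be allocated on a 2:1 basis to the waitlist or intervention group", and a single block size, "Participants will be randomised using block randomisation in blocks of 10". It describes neither varied block sizes nor keeping the size from the study team.

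The same section separates generation from the team: "A PhD student unrelated to the study will be given a list of these UIDs and use an online randomisation tool". It also says that the team has no influence over the process. The result then returns to the team: "They will then pass the list of UIDs assigned to each group to the PhD student for the study". The unique identifiers (UIDs) on the list are issued at consent. The size of each list, and when it is handed over, are not given.

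Section 2.3 (Procedure) says "Screening interviews will be carried out by the PhD student", with supervisors consulted where eligibility is uncertain. Consent comes before the screening interview. Women who pass are sent the baseline link and are then randomised. Section 2.5 says "The intervention will be delivered by a PhD student", which implies but does not state that this is the same student.

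Section 2.2 includes eligibility points that leave some room for judgement, such as an unstable health condition or substance misuse. For women with a palliative treatment plan it adds that "they will be asked if they feel well enough to participate". Section 2.2.1 gives the target: "We will aim to recruit a sample of 40 participants".

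**The concern.** Having someone else generate the sequence protects how it is made. It does not stop a person who knows the block size and has seen the earlier allocations in a block from working out what is left. If that person also screens, and so influences who enters next and when, a borderline or less well woman could be brought forward or held back according to the arm she would probably get. This need not be deliberate.

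Two features make the point worth closing. At 2:1, only about 13 of 40 women start in the intervention arm (40/3 = 13.3), so a few steered entries carry weight. The primary outcome, MARS-5, is self-reported and no blinding is described, so blinded outcome assessment is not available as a counterweight.

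A second gap adds to the first. UIDs are issued before screening. If a list of consented but unscreened women were randomised, allocations could be known before eligibility was settled. Section 2.3 implies otherwise, but 2.4 does not say so.

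**Working it through.** The plan gives no predictability figure, so there is none to reproduce.

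**Inputs.** Block size 10 and ratio 2:1 (section 2.4); 40 women, hence 4 blocks (section 2.2.1). Ten is not divisible by 3 (10/3 = 3.33), so no block of 10 can be exactly 2:1. The nearest splits, waitlist to intervention, are 7:3 and 6:4. Which one applies, or whether they alternate, is not stated.

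**1. Released singly, split constant and known.** For a block with a waitlist and b intervention places, the expected number of assignments certain before they are made is a/(b+1) + b/(a+1).
- 7:3: 7/4 + 3/8 = 2.125 per block; × 4 = 8.5 of 40.
- 6:4: 6/5 + 4/7 = 1.771 per block; × 4 = 7.1 of 40.

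**2. Released singly, split varying and unknown.** A constant 7:3 gives 28:12 over 40 women and a constant 6:4 gives 24:16. Staying close to 2:1 needs a mixture. Assume 7:3 in two thirds of blocks and 6:4 in one third. The rest of a block is then certain only after a seventh waitlist place (so it must be 7:3) or a fourth intervention place (so it must be 6:4).
- In a 7:3 block: 3/8 = 0.375 certain.
- In a 6:4 block: 6/5 = 1.2 certain.
- Average: (2/3)(0.375) + (1/3)(1.2) = 0.65 per block; × 4 = 2.6 of 40.

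**3. Released in fives, split known.** The second five is certain only if it is all waitlist, that is, if every intervention place fell in the first five.
- 7:3: 5 × C(5,3)/C(10,3) = 5 × 10/120 = 0.417 per block; × 4 = 1.7 of 40.
- 6:4: 5 × C(5,4)/C(10,4) = 5 × 5/210 = 0.119 per block; × 4 = 0.5 of 40.

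**4. Whole block released together.** None is certain.

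**5. Possible bias.** This needs a behavioural assumption that the documents do not supply. Suppose the woman entered is d better when the chance of intervention is above the block average, d worse when it is below, and neutral when equal. Enumerating every arrangement of the block, with a known split and no treatment effect, gives these expected differences in level between arms:

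| Release | 7:3 | 6:4 | At assumed d = 0.25 SD |
|---|---|---|---|
| Singly | 0.690d | 0.647d | 0.17 and 0.16 SD |
| In fives | 0.317d | 0.238d | 0.08 and 0.06 SD |
| Whole block | 0 | 0 | 0 |

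The model steers at every departure from the average probability, so for a given d it is a heavy version of the behaviour.

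**The case against.** The strongest reply is that the text on mechanics reads like batch allocation. The unrelated student works from a list and returns lists by group; CBT-I is planned in groups of about 5 (section 3.1); and the intervention group receives one recurring link. If each list is a whole block formed after baseline, nothing is foreseeable. This stands as a plausible reading. A reader might infer from 2.4 that allocation in this trial was predictable, and the documents do not support that. Equally, they do not require whole blocks, and lists of five would reduce the risk without removing it.

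A reader might also take 7 to 8.5 of 40 as the size of the problem. That needs single release and a constant, known split; with a varying split it is 2.6.

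Nor do the documents support saying that any imbalance would be invisible and beyond adjustment. SCI, PHQ-9, GAD-7, the fatigue scale and two BESS subscales are reported at baseline (section 2.7), as is MARS-5, so much of wellness is measured. Motivation is not, and the planned ANOVA names no covariates. The sample size was set on the within-between interaction (section 2.2.1). A stable difference in level moves the group main effect, and moves the group-by-time interaction only if the steered characteristic predicts change.

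Finally, screener discretion is limited. Insomnia and nonadherence use cut-offs, uncertain cases go to supervisors, and feeling well enough is the woman's own answer. These points narrow the room for steering. They do not remove control over the order and timing of entry.

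**Conclusion.** The point holds as a conditional one. Section 2.4 fixes one block size known to the study team, returns allocations to the student who on the natural reading screens, and does not require a complete block to be formed after screening and baseline and released together. If release is piecemeal, between about 0.5 and 8.5 of 40 assignments are certain in advance across the scenarios computed; if whole blocks are released, none are. Any bias is hypothetical in size: at most about 0.17 SD in level under the assumed 0.25 SD model.

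The conclusion rests on three inferences: that the screening student and the student who receives the lists are the same person, that the trial is open because it has a waitlist arm and describes no blinding, and that list size is left open. It does not depend on the screener also being the therapist, which is only implied. The plan should be changed because the remedy is nearly free and also delivers the stated 2:1, which a block of 10 cannot. Nothing in the documents shows that allocation was steered.

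**What to change.** In section 2.4, replace the blocks of 10 with allocation in complete batches. State that UIDs go to the unrelated student only once a full batch of women has passed screening and completed baseline, and that the whole batch is allocated in one random draw and released together. Use a batch size that is a multiple of 3. A batch of 15 gives 10 waitlist and 5 intervention, which meets 2:1 exactly and fills one CBT-I group of the planned size. Two batches of 15 and a last one of 9 or 12 give 39 or 42 women. This wording also settles the order of screening, baseline and allocation between 2.3 and 2.4.

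If women must be randomised one at a time, use randomly varied block sizes in multiples of 3, known only to the unrelated student and not printed in the protocol. As an illustration, simulating sizes of 6, 9 and 12 at 2:1 leaves about 0.9 of 40 assignments certain even to someone who knows the set of sizes.

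The cost is one paragraph, with the same unrelated student and the same online tool. The real downside is that women who enter early wait for the batch to fill, so their baseline is older relative to the post-intervention assessment planned about 4 weeks later. Much of that wait is already implied: at 2:1, a therapy group of about 5 needs about 15 randomised women before it can start.

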2.5. Intervention

CBT-I is a multi-component, evidence-based intervention which incorporates both cognitive and behavioural techniques to address symptoms of insomnia, aiming to improve satisfaction with the duration and quality of sleep by reducing trouble falling and/or staying asleep. Its main components include: sleep restriction, stimulus control, and cognitive restructuring. Sleep restriction aims to reduce discrepancy between time spent in bed and time actually sleeping by improving 'sleep efficiency' (SE), which is the time spent sleeping expressed as a percentage of time spent in bed. The individual is given a prescribed bedtime and waketime to match their time spent in bed with time sleeping, which is adjusted accordingly when their SE reaches 90%, or falls below 85%. Stimulus control involves strengthening the association between being in bed and being asleep, by minimising activity in the bed unrelated to sleep or intimacy, getting out of bed if unable to initiate sleep or get back to sleep after waking up, and only returning to bed when sleepy. Cognitive restructuring challenges maladaptive beliefs about sleep and concerns about the daytime consequences of poor sleep, to reduce arousal and anxiety associated with insomnia.

CBT-I will be delivered over 4 weekly 1-hour sessions, via videoconferencing. Session 1 will include psychoeducation about sleep (the relationship between sleep and mental health, the '3P' model of insomnia), and begin to explain components of CBT-I (sleep restriction and relaxation). Session 2 will reinforce previous learning about these components and introduce stimulus control. Session 3 will introduce sleep hygiene and its importance in preventing poor sleep. Session will 4 discuss cognitive therapy techniques and relapse prevention.

Participants in the waitlist condition will receive the CBT-I intervention after completing the 12-week follow-up assessment. This will then be used as a baseline measure for these participants to compare to their post-intervention and follow-up after receiving the treatment.

The intervention will be delivered by a PhD student, who will receive extensive CBT-I training from supervisors who have over 15 years' experience in delivering CBT-I. The student will receive continuous supervision throughout. Sessions will be recorded and 10% will be assessed by supervisors to monitor treatment fidelity.

2.6.2. Secondary outcomes

The Sleep Condition Indicator (SCI) measures insomnia symptoms with 8 items, scored from 0-4. Responses are summed to create a total score ranging from 0-32, with higher scores meaning better sleep. A total score of \leq 16 indicates probable insomnia disorder.

The Patient Health Questionnaire (PHQ-9) measures depressive symptoms using 9 items which each measure a different symptom. This measure is scored from 0-3, with higher scores indicating more severe symptoms. A score of ≥ 10 is recommended as a threshold for moderate to severe depression.

The Generalised Anxiety Disorder Assessment (GAD-7) measures symptoms of General Anxiety using 7 items scored from 0-3. Responses are summed to create a total score: a score of ≥ 10 indicates moderate-severe anxiety.

The Flinders Fatigue Scale (FFS) measures how often participants have felt bothered by fatigue, with 7 items where higher scores indicate worse fatigue. Six items are scored from 0-4, whereas item 5 includes a checklist which is scored from 0-7. Responses are summed to create a total score of 0-31. A score of \geq 16 indicates moderate to severe (\geq 21=severe) fatigue.

The Breast Cancer Eight Symptom Scale (BESS) includes 3 subscales: this study will use the vasomotor symptoms and musculoskeletal pain subscales. These subscales include 3 items, scored from 1-3. Scores are summed, multiplied by the number of items in the subscale, and then divided by the number of questions answered, with higher scores indicating worse symptoms.

The consensus sleep diary will be to collect self-reported data about variations in sleep for each participant. These will be completed daily (to reflect the previous night's sleep) for one week at a time. Sleep diary data will include SE, sleep onset latency (SOL), wake after sleep onset (WASO), total sleep time (TIB), time in bed (TIB), and number of night-time awakenings. All participants (intervention and control group) will complete a baseline sleep diary for one week prior to the intervention period, then complete sleep diaries throughout the 4-week intervention period.

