2.1. Design

The study is a randomised, waitlist-controlled trial of CBT-I. The advantages of a waitlist control group are: this ensures all participants have the opportunity to receive the recommended treatment for insomnia, and that by utilising control participants as intervention participants after their participation in the control condition, we can increase the statistical power of the study. The immediate intervention group will complete assessments at baseline, post-intervention (approximately 4 weeks after baseline), and after a further 8 weeks (12 weeks post-randomisation follow-up). The waitlist group will complete these assessments at the same timepoints, then 2 additional assessments after they receive the intervention, and after a further 8 weeks. The study is expected to take approximately 12 weeks from baseline

to completion (follow-up assessment). This study has been granted ethical approval has been granted from the University of Strathclyde ethics committee (UEC23/09).

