2.7 Analytic approach

Participants demographics and clinical characteristics will first be presented. Descriptive data will be presented for each outcome measure (MARS-5, SCI, GAD-7, PHQ-9, FFS and BESS subscales) and sleep diary variables at each of the 3 timepoints (baseline, post-intervention, and 12-week follow-up).

Hypotheses will be tested using a 2x3 mixed factorial ANOVA. Between-subjects factor will be group (intervention or control), and within-subjects factor will be timepoint (baseline, post-intervention, and 12-week follow-up). We will examine the main effect of group, timepoint and interaction of group and timepoint. If a significant main effect is found, subsequent comparisons will be made applying Bonferroni correction.

3. Discussion

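### No sleep diary is scheduled at the 12-week follow-up, although section 2.7 promises diary results at that timepoint

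*Combined protocol and SAP*

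**What the plan says.** Section 2.6.2 sets the diary timing for the intervention and control groups together: they "will complete a baseline sleep diary for one week prior to the intervention period, then complete sleep diaries throughout the 4-week intervention period". It describes the mode of completion as follows: "These will be completed daily (to reflect the previous night's sleep) for one week at a time". It names no diary week at follow-up.

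Section 2.7 commits to descriptive data for "sleep diary variables at each of the 3 timepoints (baseline, post-intervention, and 12-week follow-up". It also defines the 2x3 mixed ANOVA, in which the "within-subjects factor will be timepoint (baseline, post-intervention, and 12-week follow-up". It does not say which outcomes that ANOVA covers.

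Section 2.1 sets the calendar for the later assessments: "post-intervention (approximately 4 weeks after baseline), and after a further 8 weeks (12 weeks post-randomisation follow-up". It does not list what each assessment contains. Section 2.3 says only that later assessments go out by email and are completed in Qualtrics.

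Section 2.5 adds that "Participants in the waitlist condition will receive the CBT-I intervention after completing the 12-week follow-up assessment", and that this assessment becomes the waitlist arm's baseline for its own course of treatment.

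**The concern.** The collection schedule and the analysis plan cannot both be carried out as written. The schedule stops at the end of the 4-week intervention period, while the analysis plan needs diary data 8 weeks later.

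The loss would be permanent. A diary filled in each morning for the night before cannot be reconstructed once the week has gone.

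Sleep is part of the main objective in section 1, and the diary is the only listed measure that yields sleep efficiency, sleep latency, waking during the night and time in bed. Sleep efficiency is also the quantity that sleep restriction works on in section 2.5. Without a week-12 diary, the study cannot show whether gains on these measures last once the sessions end.

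There is a second effect. Section 2.5 reuses the waitlist arm's 12-week assessment as its pre-treatment baseline. On the natural reading of section 2.6.2, those women have no diary data at that baseline either.

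**Working it through.** The plan gives no figure to reproduce here, so the check compares the schedule with the promised timepoints.

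**Inputs**

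- Diary weeks scheduled: 1 before the intervention period and 4 during it (section 2.6.2).
- Diary timepoints promised: 3 (section 2.7).
- Assessments: baseline, about week 4, and week 12 (section 2.1).
- Target sample: 40 (section 2.2.1).
- Allocation: "Participants will be allocated on a 2:1 basis to the waitlist or intervention group" (section 2.4).

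**Schedule against promise**

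| Timepoint in section 2.7 | Diary week in section 2.6.2 |
|---|---|
| Baseline | Yes, the week before the intervention period |
| Post-intervention (about week 4) | Yes, if the last intervention week is used |
| 12-week follow-up | None |

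Coverage is 2 of 3 timepoints. The gap from the last scheduled diary to the follow-up is 12 − 4 = 8 weeks.

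**Women affected, by reading of section 2.6.2**

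1. *One shared block for both arms (the natural reading).* No woman has a week-12 diary: 40 of 40.
2. *The block also repeats around the waitlist arm's own treatment.* That arm's pre-treatment week could fall near week 12, but the immediate arm still has no diary. By the stated wording the immediate arm is 1/3 × 40 ≈ 13 women. If the ratio was meant the other way round, it is 2/3 × 40 ≈ 27.

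On both readings at least one arm is empty at week 12, so no between-arm diary comparison is possible there. If the 2x3 ANOVA is applied to diary variables, its third level has no data in the immediate arm and, on reading 1, none in either arm.

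**Load now and with one added week (reading 1)**

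- Now: (1 + 4) × 40 = 200 diary-weeks, or 5 × 7 = 35 entries per woman.
- Added: 1 × 40 = 40 diary-weeks, and 40/200 = 20%.
- After: 6 × 7 = 42 entries per woman.

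**Load on reading 2, if the waitlist pre-treatment week coincides with week 12**

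- Stated ratio: the base is 200 + 27 × 5 = 335 diary-weeks. About 13 are new, and 13/335 ≈ 4%.
- Reversed ratio: the base is 200 + 13 × 5 = 265 diary-weeks. About 27 are new, and 27/265 ≈ 10%.

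**The case against.** The strongest reply is that section 2.6.2 never says its list is complete. The 12-week assessment in section 2.1 is not itemised, completion in one-week blocks would suit a follow-up week, and section 2.7 plainly expects diary data then. The team may intend a week-12 diary and simply have left it out of section 2.6.2. That is possible, and it means one cannot be certain that the data will be missing. But neither section 2.1 nor section 2.3 mentions a diary, and section 2.6.2 is where diary timing is set. If a week-12 diary is intended, section 2.6.2 needs the same added sentence.

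A second reply concerns weight. The explicit diary promise is descriptive, the diary is one of several secondary outcomes in a pilot, and the SCI still measures insomnia symptoms at all three timepoints. This stands, and it limits the point. The SCI does not, however, supply the diary's night-by-night quantities.

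A third reply concerns the remedy. One student delivers treatment in groups of about 5 (sections 2.5 and 3.1), so about 27 waitlist women would make 5 to 6 groups, and starts may be staggered. The week-12 diary might then not be the week immediately before treatment. That is fair as to timing. But section 2.5 already makes the 12-week assessment this arm's baseline, so any such delay affects the questionnaires equally. A diary at that point matches the baseline the protocol has chosen.

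**Conclusion.** The concern holds. Sections 2.6.2 and 2.7 contradict each other: 1 of 3 promised diary timepoints has no scheduled collection, and the gap is about 8 weeks. If section 2.6.2 is followed as written, no woman has a week-12 diary. If it is read as repeating for the waitlist arm, the immediate arm still has none.

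The conclusion assumes that section 2.6.2 is the full diary schedule, which is reasonable because no other section sets one. The numbers of women assume that the target of 40 is met and does not fall through dropout. The consequence for the ANOVA applies only if diary variables are analysed that way.

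The effect is limited to a secondary outcome. The MARS-5, the SCI at all three timepoints and the diary comparison over the first five weeks are untouched. It should still be settled before any participant reaches week 12, because the data cannot be collected afterwards.

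**What to change.** Add to section 2.6.2 one diary week for both arms, covering the 7 nights that end at the 12-week assessment and, in the waitlist arm, falling before the first CBT-I session. State that the last intervention week serves as the post-intervention diary. The new week then fills the third timepoint in section 2.7 and gives the waitlist arm a diary at the baseline that section 2.5 assigns to it.

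It would also help to say whether the diary schedule repeats for the waitlist arm's own treatment. A further optional clarification is whether diary sleep efficiency drives the bedtime prescription, "which is adjusted accordingly when their SE reaches 90%, or falls below 85" per cent.

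The cost is one sentence and one more sending of an existing diary: 7 more entries per woman. That is 20% more diary-weeks on the natural reading, and less if the schedule already repeats and the waitlist pre-treatment week coincides with week 12. Participant burden rises slightly. The information sheet or ethics approval may need updating; the document does not say.

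The alternative is to drop the 12-week point from the diary sentence in section 2.7. That ends the contradiction at no cost in data collection, but gives up the diary evidence on whether sleep gains last. On either route, the questionnaires and the 2x3 ANOVA for them stay as they are.
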